7.3.12.1 Serum Pregnancy Test

A serum qualitative pregnancy test will be performed locally at each site on all females unless they are surgically sterile or \geq 2 years postmenopausal. On visits where required, the serum pregnancy test must be performed prior to dosing with investigational product. If the pregnancy test is positive at day 1 of cycle 1, the subject should not be given investigational product. If the pregnancy test is positive at any other visit, then investigational product must be held and a confirmatory quantitative serum pregnancy test must be done. If the confirmatory quantitative serum pregnancy test is positive, the investigational product (AMG 211) must be discontinued. If the quantitative pregnancy test is negative the subject should re-start infusion per the criteria in section 6.2.1.4.3.

7.3.13 Adverse Events

Adverse event and serious adverse event assessments will be made throughout the study and will be evaluated and recorded in the source documents and on the eCRF as specified in [Section 9.2.1](#) and [Section 9.2.2](#), respectively. Determination of the severity of all adverse events will be consistent with the CTCAE, version 4.0 ([Appendix A](#)) unless specified otherwise.

7.3.14 Pharmacokinetic Blood Sampling

Blood samples will be obtained for determination of serum concentrations of AMG 211 at the time points specified in the Schedules of Assessments ([Table 6](#), [Table 7](#), and [Table 8](#)). Blood must not be drawn from the port catheter. Sample collection, processing, storage, and shipping instructions are provided in a separate laboratory manual.

7.4 Antibody Testing Procedures

Blood samples for antibody testing are to be collected at the time points outlined in the Schedules of Assessments ([Table 6](#), [Table 7](#), and [Table 8](#)) for the measurement of anti-AMG 211 binding antibodies. Anti-AMG 211 antibodies in serum will be evaluated using screening and confirmatory assays. Samples that are confirmed positive for anti-drug antibodies will be titrated to determine the relative levels of anti-drug antibodies in the samples. Additional blood samples may be obtained to evaluate anti-AMG 211 antibodies' impact on AMG 211 exposure during the study.

Please see the laboratory manual for detailed blood sample collection and handling instructions.

7.5 Biomarker Development

Biomarkers are objectively measured and evaluated indicators of normal biologic processes, pathogenic processes, or pharmacologic responses to a therapeutic intervention. In oncology, there is a particular interest in the molecular changes underlying the oncogenic processes that may identify cancer subtypes, stage of disease, assess the amount of tumor growth, or predict disease progression, metastasis, and responses to AMG 211 and to better understand cancer.

In addition to testing the safety and effectiveness of AMG 211 in this study, the sponsor will attempt to develop tests from blood, and/or tumor biopsies (if consented) that will identify subjects that will most likely benefit from AMG 211.

Biomarker development may be pursued by use of advanced biochemical analyses, such as proteomic methods or ribonucleic acid transcript profiling.

Amgen may attempt to develop test(s) designed to identify subjects most likely to respond positively or negatively to AMG 211.

Blood Samples

Blood samples will be collected for exploratory biomarker development at the time points listed in the Schedules of Assessments ([Table 6](#), [Table 7](#), and [Table 8](#)).

For all subjects, circulating free DNA (which includes tumor DNA) will be extracted from biomarker development plasma samples collected at the time points listed in the Schedules of Assessments ([Table 6](#), [Table 7](#), and [Table 8](#)). These samples will be used to assess potential PD response to AMG 211 by measuring changes in levels of the epigenetic CRC marker methylated Septin9.

Plasma samples may also be used to explore whether expression or mutation of specific commonly occurring mutations found in tumors tissues (and other genes based on emerging data) correlates with response to AMG 211.

Immunophenotype analysis will be used to assess whole blood by flow cytometry for biomarkers which correlate with T-cell PD responses to AMG 211 and which may be used (if consented) to identify subjects that will most likely benefit from AMG 211.

The sponsor may assess blood plasma, serum, and tumor specimens for biomarkers (eg, circulating normal/tumor cells, proteins, and transcripts) that predict response to AMG 211 and help to obtain evidence for T-cell engagement and activation associated with AMG 211 treatment.

Subjects must have archival tumor tissue available or be willing to undergo biopsy of a tumor lesion. For all subjects, tumor biopsy specimens (from archival tissue or a core biopsy) may also be used for additional testing (eg, immune histochemistry and tumor mutational analyses).

These samples will be used to help identify genes and other markers that may enhance our understanding of the cancer and/or determine how subjects respond (positively or negatively) to one or more of the investigational products being investigated.

Unless consent for optional pharmacogenetic analysis has been obtained, hereditary elements will not be analyzed.

Refer to the laboratory manual for detailed collection and handling procedures for all biomarker development samples.

7.6 Pharmacogenetic Studies

If the subject consents to the optional pharmacogenetic portion of this study, DNA analyses may be performed. These optional pharmacogenetic analyses focus on inherited genetic variations to evaluate their possible correlation to the disease and/or responsiveness to the therapies used in this study. The goals of the optional studies include the use of genetic markers to help in the investigation of solid tumors and/or to identify subjects who may have positive or negative response to AMG 211. No additional samples are collected for this part of the study. For subjects who consent to this/these analysis/analyses, DNA may be extracted.

7.7 Sample Storage and Destruction

Any blood, blood derivative, or tumor sample collected for biomarker, anti-AMG 211 antibody, or PK analysis according to the Schedules of Assessments ([Table 6](#), [Table 7](#), and [Table 8](#)) can be analyzed for any of the tests outlined in the protocol and for any test necessary to minimize risks to study subjects. This includes testing to ensure analytical methods produce reliable and valid data throughout the course of the study. This can also include, but is not limited to, investigation of unexpected results, incurred sample reanalysis, and analyses for method transfer and comparability.

All samples and associated results will be coded prior to being shipped from the site for analysis or storage. Samples will be tracked using a unique identifier that is assigned to the samples for the study. Results are stored in a secure database to ensure confidentiality.

If informed consent is provided by the subject, Amgen can do additional testing on remaining samples (ie, residual and back-up) to investigate and better understand the tumor biology and the dose response and/or prediction of response to AMG 211 and characterize aspects of the molecule (eg, mechanism of action/target, metabolites). Results from this analysis are to be documented and maintained, but are not necessarily reported as part of this study. Samples can be retained for up to 20 years.

Since the evaluations are not expected to benefit the subject directly or to alter the treatment course, the results of pharmacogenetic, biomarker development, or other exploratory studies are not placed in the subject's medical record and are not to be

made available to the subject, members of the family, the personal physician, or other third parties, except as specified in the informed consent.

The subject retains the right to request that the sample material be destroyed by contacting the investigator. Following the request from the subject, the investigator is to provide the sponsor with the required study and subject number so that any remaining samples and any other components from the cells can be located and destroyed. Samples will be destroyed once all protocol-defined procedures are completed. However, information collected from samples prior to the request for destruction, will be retained by Amgen.

The sponsor is the exclusive owner of any data, discoveries, or derivative materials from the sample materials and is responsible for the destruction of the sample(s) at the request of the subject through the investigator, at the end of the storage period, or as appropriate (eg, the scientific rationale for experimentation with a certain sample type no longer justifies keeping the sample). If a commercial product is developed from this research project, the sponsor owns the commercial product. The subject has no commercial rights to such product and has no commercial rights to the data, information, discoveries, or derivative materials gained or produced from the sample.

See [Section 11.3](#) for subject confidentiality.

8. WITHDRAWAL FROM TREATMENT, PROCEDURES, AND STUDY

8.1 Subjects' Decision to Withdraw

Subjects have the right to withdraw from the study at any time and for any reason without prejudice to their future medical care by the physician or at the institution.

Subjects (or a legally acceptable representative) can decline to continue receiving investigational product and/or other protocol required therapies or procedures at any time during the study but continue participation in the study. If this occurs, the investigator is to discuss with the subject the appropriate processes for discontinuation from investigational product or other protocol required therapies and must discuss with the subject the options for continuation of the Schedules of Assessments ([Table 6](#), [Table 7](#), and [Table 8](#)) and collection of data, including endpoints and adverse events.

The investigator must document the change to the Schedules of Assessments and the level of follow-up that is agreed to by the subject (eg, in person, by telephone/mail, through family/friends, in correspondence/communication with other physicians, from review of the medical records).

Withdrawal of consent for a study means that the subject does not wish to receive further protocol-required therapies or procedures, and the subject does not wish to or is unable to continue further study participation. Subject data up to withdrawal of consent will be included in the analysis of the study, and where permitted, publically available data can be included after withdrawal of consent. The investigator is to discuss with the subject appropriate procedures for withdrawal from the study.

8.2 Investigator or Sponsor Decision to Withdraw or Terminate Subjects' Participation Prior to Study Completion

The investigator and/or sponsor can decide to withdraw a subject(s) from investigational product and/or other protocol required therapies, protocol procedures, or the study as a whole at any time prior to study completion. Subject data and the reason(s) for termination or withdrawal from the study must be documented for the final study CSR, and it may be used for the analysis of the study.

Subjects may be eligible for continued treatment with Amgen investigational product and/or other protocol required therapies by a separate protocol or as provided for by the local country's regulatory mechanism, based on parameters consistent with [Section 12.1](#).

8.3 Reasons for Removal From Treatment or Study

8.3.1 Reasons for Removal From Treatment

Reasons for removal from protocol-required investigational product(s) or procedural assessments include any of the following:

- Subject request
- Safety concern (eg, due to an adverse event, non-compliance, requirement for alternative therapy, protocol-required therapies, or pregnancy)
- Death
- Lost to follow-up
- Decision by sponsor (other than subject request, safety concern, or lost to follow-up)
- Confirmed disease progression as defined by modified irRC ([Appendix D](#)) or disease progression accompanied by worsening of symptoms or deterioration of the subject's general condition

8.3.2 Reasons for Removal From Study

Reasons for removal of a subject from the study are:

- Decision by sponsor
- Withdrawal of consent from study

- Death
- Lost to follow-up

9. SAFETY DATA COLLECTION, RECORDING, AND REPORTING

9.1 Adverse Events

9.1.1 Definition of Adverse Events

An adverse event is defined as any untoward medical occurrence in a clinical trial subject. The event does not necessarily have a causal relationship with study treatment. The investigator is responsible for ensuring that any adverse events observed by the investigator or reported by the subject are recorded in the subject's medical record.

The definition of adverse events includes worsening of a pre-existing medical condition. Worsening indicates that the pre-existing medical condition (eg, diabetes, migraine headaches, or gout) has increased in severity, frequency, and/or duration, and/or has an association with a significantly worse outcome. A pre-existing condition that has not worsened during the study, or involves an intervention such as elective cosmetic surgery or a medical procedure while on study, is not considered an adverse event.

Disease progression itself is not considered an adverse event; however, signs and symptoms of disease progression should be recorded as adverse events or serious adverse events. Deaths due to progressive disease during treatment until the Safety Follow-up Visit or 30 days after the protocol specified therapy, whichever is later, should be recorded as due to the primary tumor (eg, metastatic pancreatic cancer). If a new primary malignancy appears, it will be considered an adverse event.

The investigator is responsible for reviewing laboratory test results and determining whether an abnormal value in an individual study subject represents a clinically significant change from the subject's baseline values. In general, abnormal laboratory findings without clinical significance (based on the investigator's judgment) are not to be recorded as adverse events. However, laboratory value changes that require treatment or adjustment in current therapy are considered adverse events. Where applicable, clinical sequelae (not the laboratory abnormality) are to be recorded as the adverse event.

An adverse device effect is any adverse event related to the use of a medical device. Adverse device effects include adverse events resulting from insufficient or inadequate instructions for use, adverse events resulting from any malfunction of the device, or adverse events resulting from use error or from intentional misuse of the device.

The investigator's clinical judgment is used to determine whether a subject is to be removed from treatment due to an adverse event. In the event a subject, or subject's legally acceptable representative requests to withdraw from protocol-required therapies or the study due to an adverse event, refer to [Section 8.1](#) for additional instructions on the procedures recommended for safe withdrawal from protocol-required therapies or the study.

9.1.2 Definition of Serious Adverse Events

A serious adverse event is defined as an adverse event that meets at least 1 of the following serious criteria:

- Fatal
- Life threatening (places the subject at immediate risk of death)
- Requires inpatient hospitalization or prolongation of existing hospitalization
- Results in persistent or significant disability/incapacity
- Congenital anomaly/birth defect
- Other medically important serious event

An adverse event would meet the criterion of "requires hospitalization", if the event necessitated an admission to a health care facility (eg, overnight stay).

If an investigator considers an event to be clinically important, but it does not meet any of the serious criteria, the event could be classified as a serious adverse event under the criterion of "other medically important serious event". Examples of such events could include allergic bronchospasm, convulsions, blood dyscrasias, DILI (see [Appendix A](#) for DILI reporting criteria), or events that necessitate an emergency room visit, outpatient surgery, or urgent intervention.

9.2 Reporting of Adverse Events

9.2.1 Reporting Procedures for Adverse Events That do not Meet Serious Criteria

The investigator is responsible for ensuring that all adverse events observed by the investigator or reported by the subject that occur after the first dose of investigational product through the EOS are reported using the applicable eCRF (eg, Adverse Event Summary).

The investigator must assign the following adverse event attributes:

- Adverse event diagnosis or syndrome(s), if known (if not known, signs or symptoms),
- Dates of onset and resolution (if resolved),

- Severity (and/or toxicity per protocol),
- Assessment of relatedness to investigational product, medical devices, or other protocol-required therapy, and
- Action taken.

If the severity of an adverse event changes from the date of onset to the date of resolution, record as a single event with the worst severity on the Adverse Event Summary eCRF.

The adverse event grading scale used will be the CTCAE, version 4.0. The grading scale used in this study is described in [Appendix A](#). The investigator must assess whether the adverse event is possibly related to the investigational product, medical device(s), and/or other protocol-required therapies. This relationship is indicated by a “yes” or “no” response to the question: Is there a reasonable possibility that the event may have been caused by the investigational product, medical device(s), and/or other protocol-required therapies?

The investigator must assess whether the adverse event is possibly related to any study mandated activity (eg, administration of investigational product, protocol-required therapies, device(s) and/or procedure (including any screening procedure[s])). This relationship is indicated by a “yes” or “no” response to the question: Is there a reasonable possibility that the event may have been caused by a study activity (eg, administration of investigational product)?

The investigator is expected to follow reported adverse events until stabilization or reversibility.

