6.2.1.3 Dose-cohort Study Escalation and Stopping Rules Dose-limiting Toxicities (DLT)

A DLT will be defined as any of the following occurring in a subject during the first 28 days of treatment and regarded by the investigators and/or sponsor to be related to AMG 211. The Common Terminology Criteria for Adverse Events (**CTCAE** version 4.03) will be used to assess toxicities/adverse events.

Hematological DLTs

- ANC < $0.5 \times 10^9/L$ for ≥ 7 days
- Febrile neutropenia (fever of unknown origin without clinically or microbiologically documented infection) with ANC < $0.5 \times 10^9/L$ and fever $\geq 38.5^{\circ}\text{C}$
- Platelets < $25 \times 10^9/L$ ≥ 7 days

Non-hematological DLTs

Any AMG 211-related \geq grade 3 non-hematological toxicity excluding

- Nausea and vomiting, which is not refractory to anti-emetics
- Flare-up of pain because of potential increase in tumor volume is not regarded as a DLT
- Cytokine release syndrome manageable with symptomatic treatment and/or infusion interruption of up to 2 days

Subjects are evaluable for a DLT when they have received at least 90% of the planned doses of investigational product within the first treatment cycle (first 28 days of a cycle independent of length of the infusion) with or without the occurrence of a DLT in the 28-day safety observation period.

Any adverse event occurring outside the DLT window that is determined by the investigator to be possibly related to the investigational product, which is seen more frequently or more severe than expected or is persistent despite appropriate management, can be determined to be a DLT upon unanimous decision by the DLRT after review of the adverse event and all available safety data.

For certain toxicities such as laboratory abnormalities without a clear clinical correlation (eg, increase in serum lipase level without signs or symptoms of a clinical pancreatitis), a

discussion between the investigator and the sponsor may take place whether that adverse event should be assessed as a DLT.

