6.3 Other Protocol-required Therapies

All other protocol required therapies including corticosteroids, that are commercially available are not provided or reimbursed by Amgen (except if required by local regulation). The investigator will be responsible for obtaining supplies of these protocol-required therapies. Please also refer to [Section 6.5: Concomitant therapy](#).

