9.2.2 Reporting Procedures for Serious Adverse Events

The investigator is responsible for ensuring that all serious adverse events observed by the investigator or reported by the subject that occur after signing of the informed consent through 30 days after the last dose of investigational product or the EOS visit (whichever is later) are recorded in the subject’s medical record and are submitted to Amgen. All serious adverse events must be submitted to Amgen within 24 hours following the investigator’s knowledge of the event via the applicable eCRF.

After the protocol-required reporting period defined above, the investigator does not need to actively monitor subjects for serious adverse events. However, if the investigator becomes aware of a serious adverse event after this protocol-required reporting period, the investigator will report the event to Amgen within 24 hours of the

investigator's knowledge of the event. Serious adverse events reported outside of the protocol-required reporting period will be captured within the safety database as clinical trial cases for the purposes of expedited reporting.

The serious adverse event must be submitted to Amgen within 24 hours following the investigator's knowledge of the event via the applicable CRF. If the electronic data capture (EDC) system is unavailable to the site staff to report the serious adverse event, the information is to be reported to Amgen via an electronic Serious Adverse Event (eSAE) Contingency Report Form within 24 hours of the investigator's knowledge of the event. See [Appendix B](#) for a sample of the eSAE Contingency Reporting Form. For EDC studies where the first notification of a Serious Adverse Event is reported to Amgen via the eSAE Contingency Report Form, the data must be entered into the EDC system when the system is again available.

The investigator must assess whether the serious adverse event is possibly related to the investigational product. This relationship is indicated by a "yes" or "no" response to the question: Is there a reasonable possibility that the event may have been caused by the investigational product?

The investigator must assess whether the serious adverse event is possibly related to any study mandated activity or procedure. This relationship is indicated by a "yes" or "no" response to the question: Is there a reasonable possibility that the event may have been caused by a study activity/procedure?

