10.4.2.1 Safety Endpoints

10.4.2.1.1 Adverse Events

Subject incidence of all treatment-emergent adverse events (TEAEs) will be tabulated by system organ class (SOC) and preferred term (PT). The number and percentage of subjects reporting adverse events will be evaluated overall and by dose level and will also be tabulated by relationship to study drug.

Tables of fatal adverse events, serious adverse events, adverse events leading to withdrawal from investigational product or other protocol-required therapies, and Events of Interest (EOI) will also be provided.

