Percent change from Baseline is the arithmetic difference between post-Baseline and Baseline divided by Baseline values times 100.

Progression-Free Survival Time

Progression-free survival time is calculated as the number of days from the first administration of AMG 211 to the first assessment of disease progression as per modified irRC or clinical progression, whichever occurs first or death due to any cause, or if applicable date of censoring (date of progressive disease or death or censoring – date of study day 1 +1). Progression-free Survival Time will incorporate the independent radiologic review and/or the Investigator-reported assessment. The progression-free rate at 6 months is defined as the proportion of subjects with no disease or clinical progression at 6 months from the first administration of AMG 211.

The following censoring strategies for missing assessment dates will be used for the progression free survival analysis:

If a subject's disease has not progressed and the subject is alive, progression-free survival time will be censored at the last date they are known to be progression-free (ie, the last evaluable radiological assessment date).

If a subject has no tumor evaluation in the study, progression-free survival time will be censored at the date of the first administration of AMG 211.

Subjects who withdraw consent to participate in the study prior to disease progression will be censored at their last evaluable radiological assessment date.

Screened

A subject is considered in screening once a consent form has been signed.

Study Day

Post study day 1: study day= (date - date of Study Day 1) + 1

Pre study day 1: study day= (date – date of Study Day 1)

Study Day 1

Study day 1 is defined as the first day of administration of the investigational product after enrollment. The day prior to Study Day 1 is considered Day -1.

Treatment-Emergent Adverse Event (TEAE)

A treatment-emergent adverse event is any adverse event starting on or after the first dose of investigational product, as determined by the flag indicating if the adverse event started prior to the first dose on the Adverse Events Summary CRF, and up to and including 30 days after the end of investigational product.

Treatment-Related AE

A treatment-related AE is any treatment-emergent AE that per investigator review has a reasonable possibility of being caused by the investigational product.

Time to Progression (TTP)

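### For non-serious adverse events, one yes/no causality question covers AMG 211, devices and other required therapies, while the SAP's treatment-related tables need an answer for AMG 211 alone

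*Protocol*

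**What the plan says.** Protocol 9.2.1, on events that are not serious, lists among the attributes to be assigned: "Assessment of relatedness to investigational product, medical devices, or other protocol-required therapy". It then says that this relationship is given by a yes or no to a single question: "Is there a reasonable possibility that the event may have been caused by the investigational product, medical device(s), and/or other protocol-required therapies". A second question in the same section is wider still: "Is there a reasonable possibility that the event may have been caused by a study activity (eg, administration of investigational product".

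Protocol 9.2.2, on serious events, puts the question differently: "Is there a reasonable possibility that the event may have been caused by the investigational product". The contingency form for serious events in Protocol Appendix B likewise keeps the study drug and the device in separate columns.

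On the analysis side, SAP Section 6 states: "A treatment-related AE is any treatment-emergent AE that per investigator review has a reasonable possibility of being caused by the investigational product". SAP 10.5.1 plans subject-incidence tables for treatment-related and for serious treatment-related events by system organ class and preferred term. Protocol 10.4.2.1.1 reports events overall and by dose level, and adds that they "will also be tabulated by relationship to study drug".

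Two further sections settle what the joint question takes in. Protocol 6.3 begins "All other protocol required therapies including corticosteroids", so steroids belong to the third source. Protocol 6.1 names the devices: a portable pump, the IV bag, and an infusion line with an in-line filter.

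**The concern.** The analysis needs one fact about each event: whether AMG 211 may have caused it. For non-serious events, neither question in 9.2.1 asks for that fact by itself. The first joins three possible sources, and the second covers any study activity, including giving the drug.

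An investigator who believes that dexamethasone alone caused a mild event should answer yes under 9.2.1. The same investigator, asked about the same event as a serious one under 9.2.2, should answer no. A treatment-related table that holds both kinds of event would then apply two definitions of related, and its non-serious part would include events that the SAP's own definition excludes.

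The error need not be even across doses. Protocol 6.2.1.1 recommends steroid premedication from 800 µg/day upward. Where that is followed, events due to steroids alone fall mainly in the higher cohorts, and a by-dose table of related events could show a rise that does not come from AMG 211.

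**Working it through.** There is no plan figure to reproduce and no rate in the documents to put into a formula. The check compares what is asked with what is analysed.

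**Step 1. What each rule returns for the same cause**

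| Judged cause of the event | Non-serious: answer under 9.2.1 | Serious: answer under 9.2.2 | Status under SAP Section 6 |
|---|---|---|---|
| AMG 211, alone or with another source | yes | yes | related |
| Corticosteroid only | yes | no | not related |
| Pump or infusion line only | yes | no | not related |
| None of these | no | no | not related |

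The 9.2.2 column agrees with the SAP in every row. The 9.2.1 column disagrees in rows two and three, both times by calling an unrelated event related.

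**Step 2. What can be recovered from the composite answer**

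Write A for AMG 211, D for device, S for other required therapy, and C for the composite answer, so that C = A or D or S.

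- C = no implies A = no. Nothing is lost.
- C = yes leaves A unknown.

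If only C is stored, and n(C) non-serious events carry a yes, the count related to AMG 211 satisfies 0 ≤ n(A) ≤ n(C). A table built on C reports the upper end.

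**Step 3. The same at subject level**

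The tables count subjects. Take one preferred term at one dose level with N subjects. Let x(s) be the subjects with a serious event of that term answered yes under 9.2.2. Let x(c) be the subjects with either such a serious event or a non-serious one with a composite yes. The proportion that the SAP definition asks for lies between x(s)/N and x(c)/N, and the table would show x(c)/N. The excess is the share of subjects whose flagged events of that term are all non-serious and due only to steroids or a device.

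**Step 4. Could the excess vary with dose?**

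The planned levels are 200, 400, 800, 1600, 3200 and 6400 µg/day. The recommendation in 6.2.1.1 reaches four of these six (and any 12800 cohort), leaving out 200 and 400. Protocol 6.5, however, recommends steroids before the first dose with no dose threshold. If sites followed 6.5, low-dose subjects were premedicated too and the contrast shrinks. The two sections should be reconciled. For this point it is enough that a dose-related excess is possible, of unknown size.

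**Step 5. Which outputs use the composite answer**

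- Treatment-related table, non-serious part: exposed.
- Serious treatment-related table: not exposed, because 9.2.2 asks about the study drug alone.
- All-causality TEAE incidence, which is part of the primary endpoint: not exposed, because it does not use relatedness.
- DLT count: not exposed. Protocol 6.2.1.3 requires the event to be "regarded by the investigators and/or sponsor to be related to AMG 211", a judgement specific to the drug.

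**The case against.** The strongest reply is that 9.2.1 gives the wording of a question, not the layout of a data field. The adverse event eCRF and its completion guide are not in the documents. The and/or phrasing and the attribute list would both fit a page with one answer per source. Serious events are also reported through an eCRF and need an answer for the study drug alone, so a suitable field may already exist. The SAP definition itself presupposes such a judgement by the investigator. This stands in part: it rules out saying that the drug-related tables cannot be derived. It does not remove the mismatch, because nothing in 9.2.1 requires separate answers and the SAP names no field. The Appendix B form shows that the sponsor can separate sources, but that form is for serious events.

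A second reply is that the exposure is narrow: the non-serious part of one family of descriptive tables. That also stands.

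A reader might go further and infer that composite answers feed the DLT count and so steer escalation. The documents do not support this. No rule carries a 9.2.1 answer into the DLT definition; relatedness for a DLT is judged against AMG 211 by the investigators and/or the sponsor, and under Protocol 10.3.2 the Dose Level Review Team sees adverse events, concomitant medications and laboratory results before deciding. A reader might also take infections of a central catheter as the example. Protocol 6.1 does not list a central catheter as a device; central access appears in 6.2.1.1 only as the route. The pump and the infusion line are the device examples that the text supports, and the steroid example suffices without them.

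**Conclusion.** The point holds as a conditional one. Protocol 9.2.1 words causality for non-serious events differently from Protocol 9.2.2 and from the SAP definition. If the eCRF stores only the composite answer, the non-serious part of the treatment-related tables is biased in one direction, upward, and the tables pool two definitions of related. If the eCRF already holds a separate AMG 211 answer, and the tables are built on it, there is no numerical error, only protocol text that misdescribes what is collected.

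The size cannot be given. The documents hold no rate of events due only to steroids or a device, so only the bounds in the working apply. A larger excess at higher doses is plausible under 6.2.1.1, but 6.5 weakens the contrast. The conclusion assumes that investigators answer the question as it is worded.

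**What to change.** - **Protocol 9.2.1 and the adverse event eCRF:** replace the joint question by three yes/no answers, for AMG 211, for a medical device, and for other protocol-required therapy such as corticosteroids.
- **SAP Section 6 and 10.5.1:** derive treatment-related events from the AMG 211 answer only, and name the eCRF field used.
- **Data already collected:** query non-serious events that hold only a composite yes. Those with a no need nothing, since a composite no already means not related to AMG 211.

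If separate fields exist, the cost is about one sentence in each document. If not, it is two extra eCRF fields (three answers in place of one) plus the queries. No dosing or clinical rule changes.
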